## 6.2 IMPORTANT PROTOCOL VIOLATIONS

Data discrepancies and deviations from the CTP will be identified for all randomized subjects. Listings of protocol deviations and of unresolved discrepancies will be provided to be discussed at the combined report planning and database lock meeting (RPM/DBLM).

It will be decided whether the discrepant data can be used as they are or whether the data have to be corrected in the clinical database. Each protocol deviation must be assessed to determine whether it is an important protocol violation (PV).

For definition of important PVs, and for the process of identification of these, please refer to the Boehringer Ingelheim (BI) reference document 'Protocol Violation Handling Definitions' ([7](#)).

If any important PVs are identified, they are to be summarised into categories and will be captured in the RPM/DBLM minutes via an accompanying Excel spreadsheet ([9](#)). The following table contains the categories in which important PVs are classified. If the data show other important PVs, this table will be supplemented accordingly by the time of the RPM/DBLM.

If substantial numbers of PVs are reported at the RPM/DBLM, a decision about summarising the PVs in a tabular format will be made. Otherwise, only a PV listing will be provided.

Additionally, consistency checks will be prepared for identifying violations of time windows.

Table 6.2: 1 Important protocol violations

Category / Code	Description
A	Entrance criteria not met
A1	Inclusion criteria violated
A2	Exclusion criteria violated
B	Informed consent
B1	Informed consent not available
B2	Informed consent too late
C	Trial medication and randomisation
C1	Incorrect trial medication taken
C2	Randomisation not followed
C3	Non-compliance
C4	Medication code broken inappropriately
C5	Incorrect intake of trial medication
C6	Improper washout between treatments
D	Concomitant medication
D1	Prohibited medication use
D2	Mandatory medication not taken
D3	Improper washout of concomitant medication
E	Missing data
E1	Certain violations of procedures used to measure primary or secondary data

Table 6.2: 1 Important protocol violations (cont'd)

Category / Code	Description
F	Incorrect timing
F1	Certain violations of time schedule used to measure primary or secondary data.
G	Other trial specific important violations
G1	Incorrect intake of meal

### 6.3 SUBJECT SETS ANALYSED

All entered subjects who received study medication will be included in the safety analysis and in the PK analysis depending on the availability of measurement values, and on their adherence to the CTP.

Populations (analysis sets) and the criteria for inclusion are defined as follows:

- Randomised set (RS):  
This subject set includes all randomised subjects. It will be used for disposition displays.
- Treated set (TS):  
This subject set includes all subjects who received at least one dose of study drug. It will be used for analysis of safety, demographic data and baseline characteristics.
- Pharmacokinetic set (PKS):  
This subject set includes all subjects in the Treated Set (TS) who provide at least one primary PK parameter that is not excluded due to a relevant protocol violation or non-evaluable plasma concentrations.

According to CTP Section 7.3.1, plasma concentrations and/or parameters of a subject will be considered as non-evaluable, if for example:

- The subject experienced emesis at or before two times median  $t_{max}$  of the respective treatment (Median  $t_{max}$  is to be determined excluding subjects having experienced emesis)
- Pre-dose concentration is  $>5\%$  of the  $C_{max}$  value of that subject
- Samples/concentration data at critical phases of the PK disposition curve are missing

A subject will be included in the PKS, even if he contributes only one PK parameter value for one period to the statistical assessment.

The discussion of all exceptional cases and problems and the decisions on the allocation of subjects to populations based on other data than PK, PD or Biomarkers will be made at latest at the RPM/DBLM. Other decisions based on PK, PD or Biomarkers data have to be made once the corresponding data are assessed.

Table 6.3: 1 Subject sets analysed

Class of endpoint	Subject set		
	RS	TS	PKS
Primary and further PK endpoints		X	
Safety endpoints		X	
Demographic/baseline endpoints		X	
Disposition	X		

Note that the number of subjects with available data for an endpoint may differ. For details, see [Section 6.6](#) “Handling of missing data and outliers”.

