7.3 PLANNED ANALYSES

7.3.1 Primary endpoint analyses

All treated subjects (i.e., all subjects who received at least one dose of study drug) will be included in the treated set.

The pharmacokinetic endpoints listed in [Section 5.5.1](#) will be calculated according to the BI SOP 'Standards and processes for analyses performed within Clinical Pharmacokinetics/Pharmacodynamics' [[001-MCS-36-472](#), current version].

Plasma concentration data and parameters of a subject will be included in the statistical PK analyses, if they are not flagged for exclusion due to a protocol violation relevant to the evaluation of PK (to be decided not later than in the Report Planning Meeting) or due to PK non-evaluability (as revealed during data analysis, based on the criteria specified below). Exclusion of a subject's data will be documented in the CTR.

Relevant protocol violations may be:

- Incorrect trial medication taken, i.e. the subject received at least one dose of trial medication to which the subject was not assigned to
- Incorrect dose of trial medication taken
- Use of restricted medications (refer to [Section 4.2.2.1](#))

Plasma concentrations and/or parameters of a subject will be considered as non-evaluable, if for example:

[figure not shown]
Proprietary confidential information © 2016 Boehringer Ingelheim International GmbH or one or more of its affiliated companies

- The subject experienced emesis at or before two times median t_{max} of the respective treatment (Median t_{max} is to be determined excluding subjects having experienced emesis)
- Pre-dose concentration is $>5\%$ of the C_{max} value of that subject
- Samples/concentration data at critical phases of PK disposition curve are missing

The PK parameter analysis set (PKS) will include all subjects in the Treated Set (TS) who provide at least one primary PK parameter that is not excluded according to the description above. Thus, a subject will be included in the PKS, even if he contributes only one PK parameter value for one period to the statistical assessment.

Point estimates, the ratios of the geometric means (T/R) for the primary endpoints (see [Section 5.5.1.1](#)), and their two-sided 90% confidence intervals (CIs) will be provided.

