7.3.5 Pharmacokinetic analyses

The pharmacokinetic parameters listed in [Section 5.5.1](#) for drug BI 1467335 will be calculated according to the relevant SOP of the Sponsor ([001-MCS-36-472](#)).

Subjects who are not included in the PKS (see [Section 7.3.1](#)) will be reported with their individual plasma concentrations and individual pharmacokinetic parameters. However, they will not be included in descriptive statistics or other statistical assessments for pharmacokinetic parameters.

Only concentration values within the validated concentration range and actual sampling times will be used for the calculation of pharmacokinetic parameters. Concentrations used in the pharmacokinetic calculations will be in the same format provided in the bioanalytical report, (i.e., to the same number of decimal places provided in the bioanalytical report).

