#### **4. CHANGES IN THE PLANNED ANALYSIS OF THE STUDY**

All analyses described in this TSAP are in accordance with the statistical methods described in the CTP version 1.0.

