## 7.4 PRIMARY ENDPOINT(S)

To investigate the relative bioavailability of the two formulations (tablet/oral solution) and to investigate the effect of food on the primary PK parameters as defined in [Section 5.1](#), the following comparisons will be made:

- (1) T1 (tablet, fasted) vs. R1 (oral solution, fasted), to investigate the relative bioavailability of the tablet and solution formulations
- (2) T2 (tablet fed) vs. R2 (tablet fasted) , to investigate the effect of food on the tablet formulation

These comparisons will be performed separately on the PKS. For further details about treatments see [Table 6.1: 1.](#)

The primary PK endpoints (see CTP Section 5.5.1 and TSAP [Section 5.1](#)) will be log transformed (natural logarithm) prior to fitting the ANOVA model. For each endpoint, the difference between the expected means for  $\log(T \text{ (fasted)}) - \log(R)$  and  $\log(T \text{ (fed)}) - \log(T \text{ (fasted)})$  will be estimated by the difference in the corresponding adjusted means (Least Squares Means), and a two-sided 90% confidence interval based on the t-distribution will be computed. These quantities will then be back-transformed to the original scale to provide the point estimate and 90% confidence intervals (CIs) for each endpoint. Since the main focus is on estimation (and not testing), an acceptance range was not specified, i.e. no hypothesis will be tested.

**CTP (Section 7.1.3 Model):** *The statistical model used for the analysis of primary endpoints will be an analysis of variance (ANOVA) model on the logarithmic scale. This model will include effects accounting for the following sources of variation: 'sequence', 'subjects nested within sequences', 'period' and 'treatment'. The effect 'subjects within sequences' will be considered as random, whereas the other effects will be considered as fixed. The model is described by the following equation:*

$$Y_{ijkm} = \mu + \zeta_i + s_{im} + \pi_j + \tau_k + e_{ijkm}, \text{ where}$$

$Y_{ijkm}$  = logarithm of response (endpoint, see [CTP] Section 5.5.1) measured on subject  $m$  in sequence  $i$  receiving treatment  $k$  in period  $j$

$\mu$  = the overall mean

$\zeta_i$  = the  $i^{th}$  sequence effect,  $i = 1, 2, 3$

$s_{im}$  = the effect associated with the  $m^{th}$  subject in the  $i^{th}$  sequence,  
 $m = 1, 2, \dots, n_i$

$\pi_j$  = the  $j^{th}$  period effect,  $j = 1, 2, 3$

$\tau_k$  = the  $k^{th}$  treatment effect,  $k = 1, 2, 3$

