$e_{ijkm}$  = the random error associated with the  $m^{th}$  subject in sequence  $i$  who received treatment  $k$  in period  $j$

The analysis will be accomplished using the XPKISTAT macro, based on PKS, and the option BWC (Bioavailability/Bioequivalence, within subject design, time-controlled).

[figure not shown]

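### Does SAP Table 6.3: 1 put the primary PK analysis on the treated set and so let non-evaluable profiles in?

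*SAP*

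**What the plan says.** SAP Section 6.3 defines three sets (randomised, treated and pharmacokinetic) and then tabulates which set serves which class of endpoint. As extracted, the row "Primary and further PK endpoints" is marked under TS. Safety and demographic/baseline endpoints are also under TS, disposition is under the randomised set, and the PKS column is empty.

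The surrounding text points the other way:

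- SAP Section 6.3 on the TS: "It will be used for analysis of safety, demographic data and baseline characteristics". PK is not among these uses.
- SAP Section 7.4 on the two primary ratios: "These comparisons will be performed separately on the PKS".
- SAP Section 7.4 on programming: "The analysis will be accomplished using the XPKISTAT macro, based on PKS".
- Protocol Section 7.3.1 on which values count: "Plasma concentration data and parameters of a subject will be included in the statistical PK analyses, if they are not flagged for exclusion".
- Protocol Section 7.3.5 on subjects outside the PKS: "they will not be included in descriptive statistics or other statistical assessments for pharmacokinetic parameters".
- SAP Section 4: "All analyses described in this TSAP are in accordance with the statistical methods described in the CTP version 1.0".

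Membership of the PKS is generous: "A subject will be included in the PKS, even if he contributes only one PK parameter value for one period".

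**The concern.** A table that maps endpoints to analysis sets is a natural place for a programmer to look, and this one appears to send the primary endpoints to a set whose definition contains no PK exclusions. If the table were followed literally and nothing else applied, three kinds of period could enter the tablet/solution and fed/fasted ratios:

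- periods with emesis within twice the median tmax;
- periods with a pre-dose concentration above 5% of Cmax;
- periods with a dosing error that the Report Planning Meeting had judged relevant.

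With 18 subjects, one badly depressed profile is enough to move a geometric mean visibly. It also looks odd that a set defined in detail has no endpoint marked against it.

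**Working it through.** **1. The places side by side.**

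| Place | Set or rule for PK |
|---|---|
| SAP Table 6.3: 1 (as extracted) | TS |
| SAP 6.3, use of the TS | safety, demographic and baseline data only |
| SAP 7.4, comparisons | PKS |
| SAP 7.4, macro instruction | PKS |
| Protocol 7.3.1 | only values not flagged for exclusion |
| Protocol 7.3.5 | subjects outside the PKS kept out of all PK statistics |

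One cell stands against every other statement. The table's other three rows agree with the text of Section 6.3, so a shift of the whole table in extraction is unlikely. A shift in this one row cannot be excluded.

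**2. What the choice of set does, by type of subject.** Two rules act at different levels. The set works on subjects. The flag in Protocol 7.3.1 works on values.

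| Treated subject | In TS | In PKS | Values entering the primary model |
|---|---|---|---|
| All three profiles usable | yes | yes | all |
| Fed profile flagged (e.g. emesis), fasted profiles usable | yes | yes | fasted only |
| Only one primary parameter usable, in one period | yes | yes | that one |
| No usable primary parameter | yes | no | none |

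The sets differ only in the last row. That subject has no unflagged primary value, so he adds nothing under either label. In the second row, which is the case the worry has in mind, the flag keeps the fed profile out, and moving the X would make no difference.

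**3. The plan's own figure.** Protocol Section 7.6 gives a precision (upper/lower 90% limit, expected with 95% probability) of about 2.09 for AUC0-tz, with N = 18 and an intra-individual gCV of 58.4%.

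- σ²w = ln(1 + 0.584²) = 0.293
- df = 3N − 1 − (N − 1) − 2 − 2 = 2N − 4 = 32
- precision = exp{2 · t(0.95; 32) · √(2σ²w/N) · √(χ²(0.95; 32)/32)} = 2.085

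This matches 2.09. The other three entries also reproduce: 1.982, 1.808 and 1.890, against the stated 1.98, 1.81 and 1.89. The inputs are N and the variance, and neither depends on which column holds the X.

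**4. The feared shift.** With complete data and equal sequences, each profile has weight 1/18 in its treatment mean on the log scale. If one test profile is kept at a fraction f of its true exposure, the ratio is multiplied by f^(1/18). The values of f are assumptions; the documents give none.

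| f | Multiplier on the ratio |
|---|---|
| 0.1 | 0.880 |
| 0.2 | 0.914 |
| 0.5 | 0.962 |
| 0.8 | 0.988 |

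The arithmetic is right, but it measures what happens when a flagged value is analysed anyway. That requires Protocol 7.3.1 to be set aside. The position of the X does not bring it about: with the flag applied, the profile is absent under TS and under PKS alike.

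**The case for a change.** The best argument for acting concerns the endpoints other than the primary ones. The table row covers further PK endpoints too, whereas SAP Section 7.4 names the PKS only for the primary comparisons. SAP Section 7 gives the descriptive PK work to a separate group without naming a set. In the visible SAP text the table is then the only assignment for that work, and it names the wrong set. For these endpoints the column could matter in principle, because a subject with no usable primary parameter might still have some other usable one. The trial is also handled openly, and PK-based exclusions are decided once the data are in hand, so an unambiguous set is worth having.

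Part of this stands. The inconsistency is real on the text available, and correcting one cell would do no harm. Protocol Section 7.3.5, however, covers the descriptive case in terms: subjects outside the PKS are listed individually and left out of descriptive and other PK statistics. SAP Section 4 declares no departure from the Protocol. The SAP text on further endpoints is partly redacted, so it cannot be said that no set is named there. The point about open handling concerns when and by whom values are flagged, which the table does not govern.

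**Conclusion.** No change to the plan is needed. Read as extracted, the table entry is a misplaced mark, contradicted by the primary-analysis text of SAP Section 7.4, by the stated use of the TS in Section 6.3 and by Protocol Sections 7.3.1 and 7.3.5. It may also be an artefact of reading the table from PDF.

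The effect on both primary ratios and their 90% intervals is nil, because the only subjects on whom the two sets differ have no usable primary value. N = 18 and the planned precision of 2.09 are untouched. The shifts of about 9% and 4% (one profile at an assumed 20% or 50% of true exposure) should not be attached to this point.

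The conclusion rests on two assumptions: that values flagged under Protocol 7.3.1 are left out of the model, as that section requires, and that the descriptive work follows Protocol 7.3.5. Analysts working from SAP Section 7.4 and the Protocol would do both without any amendment.

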## **6.5 POOLING OF CENTRES**

This section is not applicable, because the study was performed in only one centre.

## **6.6 HANDLING OF MISSING DATA AND OUTLIERS**

According to section 7.4 of the CTP:

- Missing or incomplete AE times are imputed according to BI standards (see 001-MCG-156\_RD-01 ([3](#))). BI-SDTM does not contain date/time imputations, all such imputations are done during ADS generation.
- With respect to other safety evaluations, it is not planned to impute missing values.
- Missing data and outliers of PK data are handled according to BI standards (see 001-MCS-36-472\_RD-01 ([2](#))).

## **6.7 BASELINE, TIME WINDOWS AND CALCULATED VISITS**

In general, the baseline value is defined as the last measurement before the first intake of study medication.

For laboratory data, the baseline value will be derived for each treatment to be the last value before intake of study medication in the respective study period. For repeated laboratory data, baseline will be the last repetition before intake of study medication in the respective study period.

Similar for vital signs, [REDACTED] the baseline value will be derived for each treatment.

Time windows are defined in the CTP. Adherence to time windows will be checked at the RPM/DBLM.

**CTP (Section 6.1 Visit schedule):** *Exact times of measurements outside the permitted time windows will be documented. The acceptable time windows for screening, Visits 3 and 4 and end of trial examination are given in the [CTP] Flow Chart.*

*Study measurements and assessments scheduled to occur 'before' trial medication administration on Day 1 are to be performed and completed within a 3h-period prior to the trial drug administration.*

*The acceptable deviation from the scheduled time for vital signs, ECG and laboratory tests will be  $\pm 30$  min on Day 1, and  $\pm 60$  min on Day 2.*

*If scheduled in the [CTP] Flow Chart at the same time as a meal, blood sampling, vital signs and 12-lead ECG recordings have to be done first. Furthermore, if several measurements including venipuncture, are scheduled at the same time, venipuncture should be the last due to its inconvenience to subjects and possible influence on physiological parameters.*

*For planned sampling times of the PK [REDACTED] blood samples, see [CTP] Flow Chart. While these nominal times should be adhered to as closely as possible, actual sampling times will be recorded and used for determination of pharmacokinetic parameters.*

*If a subject misses an appointment, it will be rescheduled if possible. The relevance of measurements outside the permitted time windows will be assessed no later than at the Report Planning Meeting.*

## **7. PLANNED ANALYSIS**

Subjects will be assigned to treatment groups according to their randomised treatment.

Inferential statistical analyses of PK endpoints [REDACTED] [REDACTED] will be presented in Section 15.5 of the CTR and in Appendix 16.1.9.3.

Descriptive data analysis of PK endpoints will be performed by BI ClinPK/PD group and presented in Section 15.6 of the CTR. [REDACTED]

The format of the listings and tables will follow the BI guideline 'Reporting of clinical trials and project summaries' [001-MCG-159] ([7](#)).

The individual values of all subjects will be listed, sorted by sequence group, subject number and visit. All listings will be contained in Appendix 16.2 of the Clinical Trial Report (CTR). Additionally, PK [REDACTED] data will be listed in Sections 15.6 [REDACTED].

The following standard descriptive statistical parameters will be displayed in summary tables of continuous variables:

N	number of non-missing observations
Mean	arithmetic mean
SD	standard deviation
Min	minimum
Median	median
Max	maximum

For analyte concentrations as well as pharmacokinetic parameters, the following descriptive statistics will additionally be calculated:

CV	arithmetic coefficient of variation
gMean	geometric mean
gCV	geometric coefficient of variation

The data format for descriptive statistics of plasma concentrations will be identical with the data format of the respective concentrations and its descriptive statistics will be displayed according to SOP MCS-36-472\_RD1 ([8](#)).

Tabulations of frequencies for categorical data will include all possible categories and will display the number of observations in a category as well as the percentage (%) relative to the respective treatment group. Percentages will be rounded to one decimal place. The category missing will be displayed if and only if there are actually missing values. Percentages will be based on all subjects in the respective subject set whether they have non-missing values or not.

All subject data listings (SDLs), except for AE listings, will be sorted by sequence group and subject number.

Units of variables should be given in the titles or column/row descriptors in square brackets (e.g. [mg]).

## **7.1 DEMOGRAPHIC AND OTHER BASELINE CHARACTERISTICS**

Only descriptive statistics are planned for this section of the report, based on the TS presented by sequence group and overall. The following variables will be displayed: gender, race, ethnicity, age, height, weight, body mass index (BMI), smoking and alcohol status.

## **7.2 CONCOMITANT DISEASES AND MEDICATION**

Concomitant diseases will be coded according to the most recent version of the Medical Dictionary for Regulatory Activities (MedDRA). Concomitant medication will be coded according to the most recent version of the World Health Organisation – Drug Dictionary (WHO-DD).

Only descriptive statistics are planned for this section of the report.

A medication will be considered concomitant to a treatment, if it

- is ongoing at the time of administration of the respective treatment or
- starts within the on-treatment phase (see [Section 6.1](#)).

Hence a medication may be considered as concomitant to more than one actual treatment. In the listing of concomitant therapies, a record will be created for each actual treatment in which the therapy is present.

## **7.3 TREATMENT COMPLIANCE**

**CTP (Section 4.3 Treatment compliance):** *Compliance will be assured by administration of all trial medication in the study centre under supervision of the investigating physician or a designee. The measured plasma concentrations will provide additional confirmation of compliance.*

*Subjects who are non-compliant (for instance, who do not appear for scheduled visits or violate trial restrictions) may be removed from the trial and the CRF will be completed accordingly.*

It is not intended to list the compliance separately. Any deviations from complete intake will be addressed and documented at the RPM/DBLM and described in the CTR.

